## **Step 4: Uterine Cavity Access**

Once the endocervical canal has been passed, the uterine cavity will be entered.

Adequate distension of the uterine cavity and a clear visualization for examination should be ensured, and the two tubal ostiums may be correctly described.

## Step 5: Inspection of the Uterine Cavity and Tubal Ostium

A thorough inspection of the uterine cavity will be carried out, observing possible signs of pathology.

The tubal ostia will be examined for possible blockages or abnormalities in the fallopian tubes.

## **Step 6: Resolution of Benign Pathology (if applicable)**

If polyps or other benign lesions are identified, the following shall be done:

- Polypectomy: Versapoint forceps (bipolar system) or flexible scissors will be used for polyp removal.
- Biopsies: Endometrial samples will be obtained with the most appropriate technique to minimize discomfort.

## **Step 7: Hysteroscope Removal**

Once the examination or intervention is finished, the hysteroscope will be removed.

The procedure must be performed within a standard time range, avoiding unnecessary prolongation.

The duration of the test will be recorded as a variable within the study.

## 3. Postoperative

After the hysteroscope is removed, the patient will be informed of possible side effects and provided with post-operative instructions.

If the patient experiences unusual pain or symptoms, pain medication will be administered as needed and followed up prior to discharge.

## Data collection and analysis in the study

#### 1. Data Collection

Data collection will be carried out on the same day of the intervention in the hysteroscopy consultation, using a predefined Excel sheet.

Data collection personnel should have carefully read the study protocol before performing any study-related tasks.

The professionals responsible for prescribing the test should be fully familiar with the study protocol and conditions before referring patients for participation.

#### 3. Data Analysis

The data collected will be analysed using SPSS software or handed over to an external team specialised in biostatistics.

The analysis will be carried out according to the following criteria:

## 3.1. Analysis by Protocol

Only those patients who complete the study after having reached the necessary sample size will be included.

Incomplete or non-compliant data will be excluded from the analysis.

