## Complex procedures:

- Morcellator myomectomies: More complex surgical procedures, such as morcellator myomectomy, are excluded because of their level of invasion and difficulty, which could interfere with the isolated assessment of anesthesia-associated pain.
- Failure to access the uterine cavity: If adequate access to the uterine cavity is not achieved, the procedure is considered incomplete and the patient will be excluded from the study.
- Situations that prevent access to the cavity: Patients in whom hysteroscopy is failed, with cervical stenosis or other anatomical defects that completely prevent adequate access to the uterine cavity will be excluded.
- Long interventions with a large fluid passage or water balance above 1000 cc: In these cases the patient may experience additional pain due to other circumstances unrelated to the routine procedure.
- **Known uterine malformations**: Patients with uterine malformations (such as septate, unicornuate, or bicornuate uterus) will be excluded, as this could complicate access and interpretation of results, as well as affect pain tolerance during hysteroscopy.
- Waiting times longer than 60 minutes: It has been associated with an increase in pain according to the SEGO guideline for ambulatory hysteroscopy.
   Taking analgesic medication before the test: Taking medication before the test may alter the results.
- Major complication associated with the intervention: Uterine perforation, creation of false pathway or false endocervical pathway or intense bleeding (expressed as hemorrhage that requires additional maneuvers than usual for resolution).
- Failure to provide adequate informed consent in consultation or the anxiety assessment scale prior to the procedure.

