## **Summary of the Consent Delivery Procedure:**

- 1. Delivery and signature of the informed consent at the time of indication of the hysteroscopy.
- **2.** Explanation of the study and requirement of your signature for inclusion in the study, if the patient agrees to participate.
- **3.** Simple 1:1 randomization of patients using the random system proposed in the protocol. The patient's CH should be noted for the group to which she belongs.
- **4.** Explanation of the procedure again on the day of the intervention, ensuring that it is not mentioned if anesthesia will be used to avoid bias in the evaluation of pain.
- **5.** Collection of the signed consent in consultation, before the intervention, to confirm participation

This procedure ensures that all ethical and legal regulations are complied with, and that the study is conducted in a controlled manner, with minimal risk of bias, ensuring data integrity and the well-being of participating patients.

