## Randomization process

Randomization will be carried out at the time the patient presents for the intervention (in consultation, when the indication is made), after she has read and signed the informed consent. At this time, you will be randomly assigned to one of two groups (under or without anesthesia) using the system previously described.

The inclusion of the patient's procedure in the trial will be recorded by writing the name in the Clinical Judgment along with the group to which she belongs according to the randomization process. The patient will also be given the specific document of inclusion in the trial to sign after explaining what it consists of

and give him consent for the test. The documents will be sent for consultation according to the usual channels after filling in the surgical demand register appropriately as it is standardized in the unit.

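### Patients are randomised at indication, then excluded for events during or after the procedure, and only completers are analysed, so the pain comparison can lose high-pain patients, probably unequally by arm

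*Protocol*

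**What the plan says.** **Timing of allocation.** Under Randomization process: "Randomization will be carried out at the time the patient presents for the intervention (in consultation, when the indication is made". The Summary of the Consent Delivery Procedure makes it step 3, "Simple 1:1 randomization of patients using the random system proposed in the protocol", ahead of the explanation given on the day of the procedure (step 4). The sentence under Randomization process is loose, but on either reading allocation comes before the hysteroscopy.

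**Exclusions that can arise after allocation.** The list headed Complex procedures, under Exclusion Criteria, contains two kinds.

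- Known only during or after the procedure: failed access ("If adequate access to the uterine cavity is not achieved, the procedure is considered incomplete and the patient will be excluded from the study"), failed hysteroscopy, "Long interventions with a large fluid passage or water balance above 1000 cc" and "Major complication associated with the intervention: Uterine perforation, creation of false pathway or false endocervical pathway or intense bleeding".
- Possible between allocation and the start: "Waiting times longer than 60 minutes", an analgesic taken beforehand, and a missing anxiety scale.

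**Analysis set.** Section 3.1 limits the analysis to completers ("Only those patients who complete the study after having reached the necessary sample size will be included") and adds: "Incomplete or non-compliant data will be excluded from the analysis". The investigators' commitment on Data Collection and Management repeats the exclusion from analysis of patients who do not meet the criteria. Patients excluded from the study has the data of a patient rejected after inclusion removed, with the reason kept. No analysis of all randomised patients is described.

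**The concern.** An eligibility criterion can be applied safely only to facts settled before allocation. Here several criteria depend on how the procedure went, and allocation may affect that. The Introduction counts pain, with other factors, among the main reasons for failure, so at least the failed-access rule is plausibly tied to the primary outcome. If mepivacaine reduces pain, fewer treated patients should fail for pain, and control would lose more of its worst experiences.

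The primary VAS comparison is at stake first. The comparison of major complications is also weakened, as is that of surgical hysteroscopy indicated because of pain, a listed variable: some patients who would have these outcomes are removed. Reasons for exclusion and adverse events are still recorded, but no analysis of the excluded patients by arm is stated. Once VAS values have been removed, a later analysis plan cannot restore them.

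**Working it through.** **1. The plan's own figure.** Inputs from Sample size calculation: difference 1.5, SD 2.0, alpha 0.05, power 0.80. Two-sided testing is assumed from the equality null. Effect size d = 1.5/2.0 = 0.75. The two-sample t-test needs 28.9, so 29 per arm (power 0.801) and 58 in total, as stated. The enlargement is 58 × 1.10 = 63.8 and 58 × 1.20 = 69.6, giving 64 to 70. With no exclusion, power is 0.840 at 32 per arm and 0.871 at 35. The sample size is not in error.

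**2. Model for pain-related loss.** The documents give no exclusion rates, so this is an illustration. VAS is taken as normal with SD 2.0; the control mean is μ and the anaesthesia mean is μ − 1.5. A share p of patients above a cut c is lost. The control mean, c and p are assumptions. With a = (c − μ)/2 and q = 1 − Φ(a), using each arm's own mean for μ:

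- share lost = p·q
- mean of those kept = [μ − p(μq + 2φ(a))] / (1 − p·q)

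Worked case, control mean 5, c = 7, p = 1:

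- Control: a = 1, φ = 0.242, Φ = 0.841. Lost 15.9%; mean kept = 5 − 2 × 0.242/0.841 = 4.425.
- Anaesthesia: a = 1.75, φ = 0.0863, Φ = 0.960. Lost 4.0%; mean kept = 3.5 − 2 × 0.0863/0.960 = 3.320.
- Expected difference = 4.425 − 3.320 = 1.10, against a true 1.5.

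**3. Results for control mean 5.** Power is from 20,000 simulated trials per case, two-sided t-test.

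| Cut | Share lost above cut | Control lost | Anaesthesia lost | Expected difference | Power, 64 / 70 enrolled |
|---|---|---|---|---|---|
| none | – | 0 | 0 | 1.50 | 0.84 / 0.87 |
| 7 | all | 15.9% | 4.0% | 1.10 | 0.67 / 0.71 |
| 8 | all | 6.7% | 1.2% | 1.29 | 0.77 / 0.80 |
| 9 | all | 2.3% | 0.3% | 1.41 | 0.81 / 0.85 |
| 7 | half | 7.9% | 2.0% | 1.32 | 0.77 / 0.80 |
| 8 | half | 3.3% | 0.6% | 1.40 | 0.81 / 0.84 |
| 9 | half | 1.1% | 0.1% | 1.45 | 0.83 / 0.86 |

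Across control means 4 to 6 and cuts 7 to 9, the expected difference runs from 1.47 down to 0.89 if all above the cut are lost, and from 1.48 down to 1.28 if half are.

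**4. Direction.** A simpler model lets the excluded patients score k points above those kept in their arm. The mean of those kept is then the arm mean minus (share lost × k), and the difference is 1.5 − (control share − anaesthesia share) × k, with k = 2 to 3:

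- Losses 15% control, 5% anaesthesia: 1.5 − 0.10k = 1.3 to 1.2.
- Losses 5% control, 10% anaesthesia: 1.5 + 0.05k = 1.60 to 1.65.
- Equal losses: 1.5.
- No true effect, losses 15% and 5%: a spurious 0.2 to 0.3 points against anaesthesia, with a rejection rate of about 7-9% instead of 5% at 29 analysed per arm.

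The bias can therefore run either way, and the protocol's own premise makes dilution the likelier result.

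**The case against.** **No rule excludes a high VAS.** A completed procedure scored 9 stays in the analysis, so losing everyone above a cut is an extreme case. If only a quarter are lost (control mean 5), the difference is 1.42 to 1.48. This stands. The figures show a mechanism, not a forecast. The model also ignores the 0-10 limits of the scale.

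**The link to pain is indirect.** The Introduction speaks of failure in general and names pain among other factors. The exclusion list also cites stenosis and anatomical defects, and fluid balance and bleeding need not be driven by pain. This also stands. Unequal loss is an inference, and exclusions unrelated to pain cost numbers without shifting the difference.

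**Pre-start exclusions are different.** A long wait, a prior analgesic or a missing scale need not depend on arm. Agreed; they are the weaker part of the point. They still occur after allocation, so they should be reported by arm.

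**Homogeneity is deliberate.** Justification of the Criteria wants routine procedures with little variability. That supports a per-protocol sensitivity analysis. It does not support selecting the only analysis set on post-randomisation events.

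**All randomised may be unworkable.** Women who never have the procedure have no procedural VAS. This is why the minimum set below is defined as all in whom the procedure was started.

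**Conclusion.** The concern holds and should be corrected before the analysis. Randomisation before the procedure, exclusion for events during or after it, and a completers-only analysis are all fixed in the protocol text, so this is not a detail left to an analysis plan. The defect lies in the design and does not depend on the illustrative figures.

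With control mean 5, the expected difference falls from 1.5 to 1.10-1.41 if all patients above VAS 7 to 9 are lost, and to 1.32-1.45 if half are. Under full loss, cuts 7 and 8 put a true 1.5 below the 1.3 points that the protocol cites as the lower limit of a meaningful reduction (only just at cut 8). That limit informs the planning difference and is not a decision rule. The main harm is bias; the loss of power is secondary.

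**What to change.** - **Section 3.1:** make the primary analysis all randomised patients in their assigned arm; at minimum, all in whom the procedure was started, with losses before the start reported by arm and reason. Keep the per-protocol set as a sensitivity analysis.
- **Data Monitoring and Logging:** VAS collection is already planned. State that it is recorded at the end of any attempt, including failed or stopped ones.
- **Exclusion Criteria:** move the criteria that can arise after randomisation (failed access or failed hysteroscopy, fluid balance above 1000 cc, major complication, long wait, prior analgesic, missing anxiety scale) to outcomes or protocol deviations reported by arm.
- **Patients excluded from the study:** separate exclusion by the team from withdrawal by the patient. Replace the removal rule with retention of data collected up to that point, as consent and law allow.
- **Data Collection and Management commitment:** align it with the new analysis set.

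**Cost.** A protocol amendment with prior ethics authorisation, which the protocol already requires for changes, and no extra visits. No added patients are needed if the SD stays at 2.0. The VAS after an aborted attempt describes a different experience from a completed hysteroscopy, so the SD may rise. For a difference of 1.5, an SD of 2.2 gives power 0.77 at 64 and 0.80 at 70; an SD of 2.5, the top of the protocol's range, gives 0.66 and 0.70. The enrolment target should be checked against this when the amendment is written.

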## 3.2. Analysis by Subgroups

Additional factors that may influence the variability of the pain experienced will be evaluated, such as:

Age

**Parity** 

Type of pathology treated

Other relevant factors

This analysis will allow us to identify possible subgroups with significant differences in the results.

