## Justification of the relevance of the study.

In recent years, several studies have addressed pain control in hysteroscopy, many of which have explored the use of local anesthesia to relieve pain during the intervention (Nowak et al., 2024). However, despite systematic reviews and meta-analyses on the effectiveness of these interventions, evidence in this field remains limited and scattered, especially with regard to well-designed, controlled clinical trials (Ahmad et al., 2017). For example, although some studies have shown that intracervical anesthesia significantly reduces pain during hysteroscopy, heterogeneity in pain assessment methods, the type of anesthesia used, and patient characteristics make it difficult to generalize the results (Cooper et al., 2010; De Silva et al., 2020).

In addition, Cochrane reviews show that there is a lack of sufficient evidence to show that different anaesthesia modalities have significantly different effects or whether anaesthesia is actually beneficial in all cases (Cochrane, 2020). The 2021 clinical practice guideline of the Spanish Society of Gynecology and Obstetrics (SEGO) recommends the use of anesthesia only when hysteroscopes larger than 5 mm are used, with a low quality of evidence. In this same document, it is highlighted that, although the differences found in other studies are statistically significant, they do not seem to be clinically relevant for the reduction of pain during the procedure or at 30 minutes post-procedure, since the differences are small and do not reduce the number of vagal symptoms (Pascual Pedreño et al., 2021). These differences are more significant in postmenopausal women, highlighting the need for a higher-quality randomized clinical trial that provides strong evidence on the benefits of pain management during hysteroscopy.

Some national surveys, such as the one conducted by Huang et al. (2023), reveal that only slightly more than half of hysteroscopies are performed under anesthesia, underscoring the disparity in clinical practice globally. In neighbouring countries, several authors have already pointed out this variability in the application of anaesthesia and suggest the need to establish clear recommendations through national and international guidelines (De Silva et al., 2020).

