## **Clinically Relevant Difference:**

• In previous studies, a reduction of at least 1.3 - 1.5 points in VAS has been considered to be clinically meaningful in gynecological procedures. □ Proposal: Establish an expected difference of 1.5 points in the VAS.

**Standard deviation** of pain in hysteroscopy without anesthesia:

According to previous studies, the standard deviation of pain ranges from 1.8 to 2.5 points in VAS.

Proposal: Use a standard deviation ( $\sigma$ ) of 2.0 for the calculation.

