## Level of significance:

It is set at 5% (0.05), which implies a probability of type I error of 5% (rejecting the null hypothesis when it is true).

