## **Statistical power:**

The statistical power is set at 80% (0.8), which implies a 20% probability of type II error (not detecting a real difference).

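### Section 3.2 promises to identify subgroups by significance from an open list of factors, which 29 patients per arm cannot do reliably by within-subgroup or interaction tests

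*Protocol*

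**What the plan says.** Section 3.2 (Analysis by Subgroups) begins: "Additional factors that may influence the variability of the pain experienced will be evaluated, such as". It names age, parity and type of pathology treated, and ends the list with "Other relevant factors". It then states what the analysis will deliver: "This analysis will allow us to identify possible subgroups with significant differences in the results".

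The section gives no test, no cut-points and no exploratory label. The only between-group test in the protocol is in Sample size calculation: Student's t-test, or Mann-Whitney U if the data are not normal. The opening of Selected variables adds that the recorded variables may also serve for subgroup work. The background (Justification of the relevance of the study) says of effects in earlier work: "These differences are more significant in postmenopausal women". Menopausal status is not named in section 3.2, although age of menopause is recorded under Patient variables.

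**The concern.** The criterion offered for finding a subgroup is statistical significance. Significance in one subgroup and not in another is not evidence that the effect differs between them. In a trial of this size it mostly reflects chance and subgroup size. An open list adds to this, because every further factor is another opportunity for such a pattern.

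At stake are claims such as anaesthesia working in parous but not in nulliparous women when the effect is the same in both. The section Importance of a well-designed clinical trial wants the results to support recommendations for practice. The primary comparison is not affected.

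**Working it through.** **Inputs.** Two-sided alpha 0.05 (Level of significance; two-sidedness is assumed because H0 is an equality of means). Power 0.80 (Statistical power). Difference: "Establish an expected difference of 1.5 points in the VAS". SD 2.0, from a stated range of 1.8 to 2.5. Range of the difference: "a reduction of at least 1.3 - 1.5 points in VAS has been considered to be clinically meaningful". Sample size 29 per group, 58 in total, or 64 to 70 with allowance for losses (Final Estimate).

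**1. The plan's own figure.** With a difference of 1.5 and SD 2.0, noncentral-t power is 0.787 at 28 per group and 0.801 at 29. The stated 29 per group is reproduced.

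**2. Reading A: the t-test is repeated in each subgroup.** Take a two-level factor split evenly, and a true effect of 1.5 in everyone.
- Patients per arm in each half: 58/4 = 14.5.
- Standard error of the difference in one half: 2.0 × √(2/14.5) = 0.743. Noncentrality: 1.5/0.743 = 2.02. The critical value at 27 df is 2.05.
- Power in each half: p = 0.495.
- Exactly one half significant: 2p(1 − p) = 2 × 0.495 × 0.505 = 0.500.
- Both significant: 0.495² = 0.245. Neither: 0.505² = 0.255.

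A simulation of 8,000 trials gave 0.493 for exactly one.

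**3. Sensitivity of Reading A.** For unequal subgroups the formula is p1(1 − p2) + p2(1 − p1). Over totals of 58 to 70, SD 1.8 to 2.5, differences 1.3 to 1.5 and splits from 50/50 to 25/75, it runs from 0.396 (N 58, SD 2.5, difference 1.3, even split) to 0.600 (N 58, SD 1.8, difference 1.5, 25/75 split).

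The rate depends on the true effect. For an even split, N 58 and SD 2.0:

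| Uniform true effect | Power per half | Exactly one half significant |
|---|---|---|
| 0 | 0.050 | 0.095 |
| 0.5 | 0.100 | 0.18 |
| 1.0 | 0.255 | 0.38 |
| 1.5 | 0.495 | 0.50 |
| 2.0 | 0.738 | 0.39 |
| 2.5 | 0.900 | 0.18 |

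**4. Several factors under Reading A.** For three independent, evenly split factors at the design effect, the same simulation gave 0.75 for at least one factor with exactly one half significant. This is below 1 − 0.5³ = 0.875 because all factors are tested on the same outcomes. Correlated factors would give a different figure.

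**5. Reading B: an interaction test.**
- Standard error of the difference between the two subgroup effects: 2.0 × √(4/14.5) = 1.05 VAS points.
- False-positive rate under a uniform effect: 0.05 per factor; 1 − 0.95³ = 0.143 over three independent factors (simulated 0.144).
- Power for a 1.5-point interaction: 1.5/1.05 = 1.43, giving 0.289 at 54 df (0.297 by the normal approximation).
- Power reaches 0.80 only at an interaction of about 3.0 points (0.801), twice the design difference.
- With all 70 patients analysed: standard error 2.0 × √(4/17.5) = 0.96, power 0.34 for 1.5 points.

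**The case against.** **The protocol does not prescribe within-subgroup tests.** A reader might infer a written rule of testing treatment in each subgroup and comparing p-values. No such rule is there. The opening of section 3.2 speaks of factors that affect pain, and Objectives of the study plans a regression for that purpose, so part of the section may be prognostic. This stands, and Reading A is therefore conditional. It remains a natural reading: the section is headed as a subgroup analysis, its product is subgroups with significant differences, and no other between-group test is named.

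**The test, cut-points and multiplicity belong in the SAP.** This also stands, and their absence is not the point. The point is what the protocol does state: a significance criterion, an open list, and a claim about what the analysis can deliver. A SAP with interaction tests on a closed list would have to depart from that text.

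**One half is not a general rate.** A reader might infer that any uniform effect gives a false subgroup finding half the time. It does not. For an even split, 2p(1 − p) cannot exceed 0.50, and the design effect sits at that maximum. The background itself calls earlier differences small. Nor does the open list produce the per-factor figure, which comes from low power within subgroups. The list raises only the chance across factors.

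**Menopausal status.** Not naming it is a minor matter. The list is introduced by way of example, so it could be added.

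**Conclusion.** The point holds in conditional form. Read as repeated tests within subgroups, a uniform 1.5-point effect would give significance in exactly one half of an evenly split two-level factor in about 50% of trials, and in about 40% to 60% over the protocol's own planning ranges and splits down to 25/75. At zero effect the figure is 9.5%. Across three independent such factors at the design effect, at least one discordant result is expected in about 75% of trials. Read as an interaction test, the false-positive rate is 5% per factor, but power is only about 29% for an interaction as large as the design difference.

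The statement that subgroups can be identified is therefore not supported by this design on either reading. The results rest on SD 2.0, two-level factors, two-sided 5% tests and 58 analysed patients unless stated otherwise. The text should be changed, but the defect concerns secondary claims only.

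**What to change.** Replace the list and the closing sentence of section 3.2 with wording to this effect:

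*Effect modification will be explored for age (continuous), previous vaginal deliveries (0 versus 1 or more) and menopausal status (derived from the recorded age of menopause). For each factor in turn, VAS will be regressed linearly on treatment, the factor and their product. The interaction estimate will be reported with its 95% confidence interval as exploratory. P-values within subgroups will not be used to claim a subgroup effect.*

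The three factors are examples; what matters is that the list is short, closed and made of baseline factors. The open final item should be deleted. Type of pathology treated is left out because it is settled during the hysteroscopy, after randomisation. The linear regression has to be added for this purpose, since the protocol currently has only the two-group test and a logistic regression.

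The cost is wording in the protocol and SAP, with no new data. The downside is that fewer subgroup claims can be made. The change lowers the false-finding rate but does not raise power, so wide intervals should be expected.
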